#### 4. ANALYSIS SETS (POPULATIONS FOR ANALYSIS)

Participant Analysis Set	Description	Applicable Analysis (for additional information refer to Section 6)
Enrolled	All participants who sign the informed consent document and enroll in this open-label extension (OLE) study.	Screening, Disposition, Protocol Deviations
Safety Analysis Set	All enrolled participants who have received at least one dose of study drug in this OLE study. Participants will be analyzed according to the assigned daily maintenance dose on study day 1 in the OLE study.	Demographics, Baseline characteristics, SCD History, Medical history, SCD complications history, Adverse events, Exposure, Prior and Concomitant medications, Labs, Potential Hy's Law cases, VOC, Pharmacodynamic endpoints, Weight, PROs
PK Analysis Set	All enrolled participants who receive at least one dose of study drug and have at least one measurable concentration data point (plasma or whole blood).	Whole blood and plasma concentrations

#### 5. GENERAL METHODOLOGY AND CONVENTIONS

##### 5.1. Definition and Terminology

- Day 1 is the day of first dose of C5351005 study drug administration.
- EOT information is collected on the C5351005 EOT eCRF page. The EOT date from this form will serve as the last dose of study (eg for defining TEAE etc).
- Date of study completion/discontinuation is the study completion/discontinuation date from C5351005 EOS eCRF page. If this date is missing, date of last known assessment will be used.
- Study Day is defined relative to the C5351005 date of first dose of study drug, i.e., Day 1.

For study assessments or events that occur on or after the date of first dose of study drug, the study day of an assessment/event is calculated as:

Study Day = event date – date of first dose + 1.

For pre-treatment events, the study day is calculated as:

Study Day = event date – date of first dose.

- Study Visit is the nominal visit as recorded on the CRF.
- Visit windows rules are defined in Appendix 1. No windowing rules will be applied to PK endpoints where only nominal visits will be used for presentation purposes.
- Treatment of Outliers for Pharmacokinetic Data

Individual blood and plasma concentration-time points, if considered anomalous, may be excluded from the analysis at the discretion of the pharmacokineticist following a review of the available documentation.

Entire individual treatment profiles for any participant, if considered anomalous, may be excluded following review of the available documentation and discussion with the Sponsor. However, results of analysis with and without the excluded profiles may be presented in the CSR.

Any such exclusion or treatment of anomalous PK data, as described above, will be discussed with the Sponsor's Clinical Pharmacologist and clearly described in the CSR along with justification for exclusion.

## 5.2. Hypotheses and Decision Rules

No formal statistical hypothesis testing will be performed in C5351005 study. All statistical analyses will be used for estimation purposes only and as such no decision rules are required. All p-values will be considered descriptive in nature and will not be used for inference.

## 5.3. General Methods

Data in general will be summarized as follows unless stated otherwise:

Participants without delayed start				Participants with delayed start				All Participants			
100 mg	150 mg	200 mg	Total	100 mg	150 mg	200 mg	Total	100 mg	150 mg	200 mg	Total

- Participants can be classified into two groups: (1) Participants without delayed start (2) Participants with delayed start.

- Participants with delayed start are those with a gap in dosing > 42 consecutive days from completing the originating study (Date of first dose in C5351005 – EOT date from parent study + 1 > 42).
- Participants without a delayed start are those with a gap in dosing ≤ 42 consecutive days from completing the originating study (Date of first dose in C5351005 – EOT date from parent study + 1 ≤ 42 days)
- Dose groups will be defined using the assigned daily maintenance dose in the C5351005 on study day 1 (SD\_1 CRF form).
- Total columns will not be presented for PK outputs.
- All figures (unless stated otherwise) will be provided for each group and all participants. In each figure, data will be presented for each dose arm and total.

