## 2.1. Schedule(s) of Assessments and Procedures

### Adult Participants with Delayed Start of Open Label Extension (OLE) Study (>42 days)

**Table 1. Schedule of Assessments for Adult Participants with Delayed Start of OLE (>42 days)**

		Treatment Period										
Study Week	Baseline visit	1	2	4	6	8	12	16	20	24	Every 12 weeks	EOS  /ET
Study Day	1 (± 30)	7 (± 3)	14 (± 3)	28 (± 3)	42 (± 3)	56 (± 3)	84 (± 7)	112 (± 7)	140 (± 7)	168 (± 7)	252+ (± 14 Days)	
Informed consent/assent	X											
Eligibility assessment	X											
Medical history	X											
Physical examination a	X						X			X	X	X
Height	X											
Weight	X						X			X	X	X
Vital signs b	X	X	X	X	X	X	X	X	X	X	X	X
Serology (hepatitis A, B, C, HIV) only if clinically indicated	X											
Hematology including reticulocyte count and serum chemistry	X		X	X	X	X	X	X	X	X	X	X
aPTT, INR, PT	X											
Serum erythropoietin	X						X			X	X	X
eGFR c	X									X	X	X
Urinalysis	X						X			X	X	X

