**Table 1. Schedule of Assessments for Adult Participants with Delayed Start of OLE (>42 days)**

		Treatment Period										
Study Week	Baseline visit	1	2	4	6	8	12	16	20	24	Every 12 weeks	EOS  /ET
Study Day	1 (± 30)	7 (± 3)	14 (± 3)	28 (± 3)	42 (± 3)	56 (± 3)	84 (± 7)	112 (± 7)	140 (± 7)	168 (± 7)	252+ (± 14 Days)	
Dispense study drug	X						X			X	X	
Return unused study drug k		X	X	X	X	X	X	X	X	X	X	X
Concomitant medication	X	X	X	X	X	X	X	X	X	X	X	X
Serious and nonserious AE monitoring	X	X	X	X	X	X	X	X	X	X	X	X

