Instructions for recording VOC events and source document collection for VOC event adjudication are provided in Section 9.4.12.1.

For participants with a gap in dosing >42 consecutive days from completing the originating study, outcome measures will be evaluated at the end of the loading dose period (Week 1), then every 2 weeks for the first 2 months (up to Week 8), then every 4 weeks for 4 months (up to Week 24), then every 12 weeks thereafter.

For participants from Part A of C5351004 or any other open label osivelotor study, outcome measures will be evaluated every 12 weeks.

For participants from Part B of C5351004, or any other randomized, blinded, placebo controlled osivelotor study, outcome measures will be evaluated every 8 weeks for the first 24 weeks of treatment in the open label study, and every 12 weeks thereafter.

For pediatric participants from Part C of C5351004, outcome measures will be evaluated at Week 2 and Week 4, then every 4 weeks for the first 24 weeks of treatment, and then every 12 weeks thereafter.

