#### 9.3.3. Clinical Laboratory Tests

Blood and urine for clinical laboratory tests (Table 9) will be collected as outlined in the SoA (Section 2.1). A certified central laboratory will be utilized to process and provide results for the clinical laboratory tests. The Baseline laboratory test results for clinical assessment for a particular test will be defined as the last measurement prior to the first dose of study drug.

Prior to initiation of treatment, if a participant has an out-of-range value for a clinical laboratory parameter that the Investigator believes is not clinically significant or that the Investigator does not believe is correct (eg, laboratory or specimen processing error), but the Investigator wants to confirm with a repeat laboratory test, a single repeat is allowed to confirm the initial result.

All out of-range values will be assessed by the Investigator as clinically significant or not clinically significant. For any laboratory test value outside the reference range that the Investigator considers clinically significant during the on-study period (ie, following dose administration), the Investigator will repeat the test to verify the out-of-range value and

clinical significance. Clinically significant laboratory abnormalities will be recorded in the AE eCRF (see Section 9.4.7.2).

For pediatric participants,

- Blood draws will be minimized (see Section 9.3.3.1).
- Encourage pain management techniques, for example, cold spray, lidocaine cream, Buzzy Bee, massage, guided imagery, heat/cold packs.
- Reduce fear by providing comfort items/swaddling, parental presence, medical play therapy so children know what to expect, distraction (toys, videos, music), and/or provide a reward system after necessary painful procedures.

See Section 11.4 for suggested actions and follow-up assessments regarding liver safety in the event of potential DILI.

See Section 11.5 for guidelines on laboratory testing to monitor kidney function and reporting laboratory test abnormalities.

Additional safety laboratory tests may be conducted as needed by the Investigator to evaluate participant safety.

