**2.2.3. Study Design**

C5351005 (OLE) is designed as a multicenter, global, open-label extension study. The primary objective is to assess the long-term safety of osivelotor in participants with SCD. This study is available to eligible participants who have previously enrolled in a Pfizer-sponsored osivelotor clinical study and meet the entry criteria for this study.

Eligible participants will receive open-label osivelotor at Baseline (Day 1). It is intended that Day 1 coincides with the final visit from the originating osivelotor study. End of Treatment (EOT) assessments from the originating study will serve as Baseline assessments for this study. If Day 1 for this study is greater than 7 days from the completion of the originating study, new baseline assessments will be obtained. If during the period between Day 1 of this study and completion of the originating study no dose is received for greater than 3 consecutive days, an appropriate loading dose will be administered prior to continued maintenance dosing.

Only participants from C5351004 Part A (also referred to as the “parent study”) were enrolled into the OLE. C5351004 Part A is a study which enrolled only adult participants. There are two sets of participants rolling over from C5351004 Part A to the OLE study – (i) participants without a delayed start (Date of first dose in C5351005 – EOT date from C5351004 + 1 ≤ 42 days) and (ii) participants with a delayed start of OLE (Date of first dose in C5351005 – EOT date from C5351004 + 1 > 42 days). Each set follows a distinct schedule of assessments as outlined in the C5351005 protocol.

**3. ENDPOINTS AND BASELINE VARIABLES: DEFINITIONS AND CONVENTIONS****3.1. Primary Endpoint(s)****3.1.1. Incidence of TEAEs**

A treatment-emergent adverse event (TEAE) is defined as an AE that occurs during the effective duration of treatment defined as the time from the first dose of study drug through last dose of study drug + 56 days.

TEAEs that occur in the parent study are not counted as TEAEs in this study. In case, the start date of AE is the same date as the treatment start date and the question in the AE CRF page “Is this AE continuing from the parent study?” = “Yes”, then the event is not a TEAE,

as long as it can be confirmed that the AE in question had a start date in the parent study and no end date in the parent study.

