**Table 3: Analysis visit windows for participants with delayed start: labs (hematology and chemistry)**

Analysis Visit Time	Target Study Day	Per Protocol Study Day Range	Study Day Range for Statistical Analysis*
Baseline visit	1	[-29, 31]	[**, 1]
Week 2	14	[11, 17]	[2, 21]
Week 4	28	[25, 31]	[22, 35]
Week 6	42	[39, 45]	[36, 49]
Week 8	56	[53, 59]	[50, 70]
Week 12	84	[77, 91]	[71, 98]
Week 16	112	[105, 119]	[99, 126]
Week 20	140	[133, 147]	[127, 154]
Week 24	168	[161, 175]	[155, 210]
Week 36	252	[238, 266]	[211, 294]
Week 48	336	[322, 350]	[295, 378]
Week 60	420	[406, 434]	[379, 462]
Week 72	504	[490, 518]	[463, 546]
Week 84	588	[574, 602]	[547, 630]
Every 12 weeks	672	[658, 686]	...
.....			

\*If multiple assessments occur within a visit window, then the average of those assessments will be used for summarization and analysis.

\*\* Refer to Appendix 1.2 for baseline derivation rules

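### Whole-study TEAE tables set delayed-start and non-delayed participants side by side although scheduled ascertainment to Week 24 is 9 AE checks and 8 laboratory draws against 2 and 2

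*SAP*

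**What the plan says.** SAP Section 2.2.3 states that only participants from C5351004 Part A were enrolled. It divides them by whether the first extension dose came more than 42 days after the end of parent-study treatment, and adds: "Each set follows a distinct schedule of assessments as outlined in the C5351005 protocol".

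SAP Section 5.3 carries the split into the displays: "Participants can be classified into two groups: (1) Participants without delayed start (2) Participants with delayed start". The default layout has columns for each group by dose, then the same columns for All Participants. Section 6.1.1 uses this layout for TEAEs. Under Section 5.3.1 the denominator is the number of participants in the column.

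The schedules are in the protocol. Section 9.2 says that after a gap of more than 42 days "outcome measures will be evaluated at the end of the loading dose period (Week 1), then every 2 weeks for the first 2 months", then every 4 weeks to Week 24 and every 12 weeks thereafter. For the others: "For participants from Part A of C5351004 or any other open label osivelotor study, outcome measures will be evaluated every 12 weeks". Tables 1 and 2 carry this into the rows "Serious and nonserious AE monitoring" and "Hematology including reticulocyte count and serum chemistry".

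Scheduled tests can generate AEs. Protocol Section 9.3.3 states: "Clinically significant laboratory abnormalities will be recorded in the AE eCRF". Section 9.3.2 does the same for confirmed, clinically significant vital-sign abnormalities.

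**The concern.** The number of recorded TEAEs depends partly on how often someone looks. For the first 24 weeks one group is looked at about four times as often as the other, and the SAP attaches no consequence to this in its TEAE summaries. It plans no split by onset period, no caution beside the tables and, under Section 6.4, no subset analyses.

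Delayed-start participants also restart after a long gap with a loading dose, so a reader will naturally look to these columns for a restart effect. A real effect and a detection effect would both fall in the first months, and a whole-study table cannot separate them. TEAE incidence is a primary endpoint and all conclusions are descriptive, so comparability of adjacent columns matters even without a test.

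**Working it through.** **Scheduled assessments to Week 24.** Inputs are the marked cells in Protocol Tables 1 and 2, excluding baseline.

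- Delayed, AE checks: Weeks 1, 2, 4, 6, 8, 12, 16, 20, 24 = 9.
- Delayed, hematology/chemistry: the same weeks without Week 1 = 8.
- Non-delayed, AE checks: Weeks 12, 24 = 2.
- Non-delayed, hematology/chemistry: Weeks 12, 24 = 2.

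The text of Protocol Section 9.2 agrees: 1 (Week 1) + 4 (Weeks 2 to 8) + 4 (Weeks 12 to 24) = 9, and 24/12 = 2. So do the SAP analysis windows through Week 24: 9 for vital signs in the delayed group (SAP Table 2), 8 for laboratory data (SAP Table 3) and 2 for the non-delayed group (SAP Table 5). Protocol Section 3.2.1 leaves out the Week 1 visit, which would give 8 visits. Table 1, Section 9.2 and SAP Table 2 all include it, so 9 stands.

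The ratios are 9/2 = 4.5 for AE checks and 8/2 = 4 for draws. After Week 24 each group adds one visit per 12 weeks, so the cumulative counts converge in ratio:

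| By week | AE checks | Draws |
|---|---|---|
| 24 | 9 vs 2 | 8 vs 2 |
| 48 | 11 vs 4 | 10 vs 4 |
| 84 | 14 vs 7 | 13 vs 7 |

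**Illustration of draw overlap.** Assume one silent laboratory abnormality lasting d weeks, with onset uniform over Weeks 0 to 24, and scheduled draws only. A draw at week t overlaps it if onset lies between t − d and t. The delayed group has four draws 2 weeks apart and then four draws 4 weeks apart; the non-delayed group has two draws 12 weeks apart. The overlap chances are therefore:

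- delayed: [4 × min(d, 2) + 4 × min(d, 4)] / 24
- non-delayed: 2 × min(d, 12) / 24

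| Duration (assumed) | Delayed | Non-delayed |
|---|---|---|
| 1 week | (4 + 4)/24 = 33% | 2/24 = 8% |
| 2 weeks | (8 + 8)/24 = 67% | 4/24 = 17% |
| 4 weeks | (8 + 16)/24 = 100% | 8/24 = 33% |
| 8 weeks | 24/24 = 100% | 16/24 = 67% |
| 12 weeks | 24/24 = 100% | 24/24 = 100% |

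These are chances that a draw falls within the abnormality. They are not TEAE rates.

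**Which columns are exposed.** Within each group's columns all doses share one schedule, so dose comparisons there are unaffected. Under All Participants, dose columns are affected only if the delayed/non-delayed mix differs by dose. The documents do not give that mix.

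**The case against.** The strongest reply is that no delayed versus non-delayed comparison is planned. SAP Section 5.2 specifies no hypothesis test or decision rule, and no estimand contrasts the groups. Showing them in separate columns is already partial handling. This stands: the point is about interpretation, not error rates.

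The overlap figures also do not carry over to TEAEs. An abnormal result becomes an AE only if the investigator judges it clinically significant, and the test is repeated to verify it. Protocol Section 9.4.7.2 says that the same abnormality is not recorded again at each visit unless its severity, seriousness or etiology changes, and SAP Section 6.1.1 counts a participant once per preferred term. Investigators may order extra safety tests. AEs are collected over the whole interval between visits by open-ended questioning (Protocol Sections 9.4.7 and 9.4.10), so 9 versus 2 checks overstates the difference for events that participants remember. All of this stands. It leaves mild, transient and laboratory-detected events as the exposed part.

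A reader might infer that the groups should be compared or pooled only after Week 24, or early on only for serious and Grade 3 or higher events. The documents do not support that. The primary estimand takes in all data from consent onward, and Protocol Section 10.3.1 calls for overall reporting. The restriction would also limit comparison in the period when a restart effect would be most likely to show. Nor is Grade 3 or higher independent of the schedule, since some laboratory values, such as creatinine (Protocol Section 11.5.4), are graded directly.

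**Conclusion.** The concern holds in a limited form. Scheduled ascertainment to Week 24 is 9 and 8 against 2 and 2, the later schedules match, and the SAP makes no allowance for this in its TEAE summaries. A higher incidence of mild or laboratory-detected TEAEs in the delayed group could partly reflect more frequent ascertainment. Serious TEAEs should be least affected.

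The size of the effect on TEAE incidence cannot be derived, because the share of TEAEs that are found only by scheduled testing is not given. The illustration rests on assumed durations, uniform onset and scheduled draws alone.

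Two stronger readings are not supported. One is that any excess in the delayed group is a detection artefact: those participants also restart after a gap with a loading dose, so part of a difference could be real. The other is that every dose comparison is distorted: only the All Participants dose columns can be, and only under an unequal mix. This is an inexpensive improvement to the reporting; it does not undermine the primary analysis.

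**What to change.** Keep all planned TEAE tables and the all-data estimand, and do not restrict pooling or comparison. In SAP Section 6.1.1:

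- Add supplementary repeats of the overall TEAE table, the SOC/PT table and the serious TEAE table by onset period: Day 1 to Week 24, and after Week 24. For the later period use participants still in the TEAE window at Week 24 as denominator.
- Add a simple rule assigning events with partial or unknown start dates to a period. SAP Section 5.4.1.4 says that no imputation of AE start dates is needed to define a TEAE, so no rule exists for this split.
- Footnote the scheduled AE checks and draws per group (9/8 versus 2/2). State that first-period differences between the groups in non-serious and laboratory-detected TEAEs should be read with the unequal schedules in mind, serious TEAEs being least affected.

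The footnote alone would not let a reader see the groups over a period with matching schedules; the onset split does.

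The cost is SAP wording, one date rule and a few extra tables with fewer events in each. No new visits or data are needed. One limitation should be stated: the later-period denominator conditions on remaining in the TEAE window, so it describes a selected set of participants.

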## 5. STUDY DESIGN

### 5.1. Overall Design

This multicenter, global, open-label extension study is designed to assess the safety of long-term treatment with osivelotor in participants with SCD. The study will be conducted globally and will be available to eligible participants enrolled in a prior Pfizer-sponsored osivelotor clinical study (originating study). Participants must meet the entry criteria for this

study to be eligible for enrollment (see Section 6.1). The study will have a global distribution, and up to approximately 500 participants will be enrolled.

Eligible participants will receive osivelotor administered orally daily if they continue to receive clinical benefit that outweighs risk, as determined by the Investigator, until the participant has access to osivelotor from an alternative source (eg, through commercialization or a managed-access program).

Eligible participants will receive open-label osivelotor at Baseline (Day 1). It is intended that Day 1 coincides with the final visit from the originating osivelotor study. End of Treatment (EOT) assessments from the originating study will serve as Baseline assessments for this study. If Day 1 for this study is greater than 7 days from the completion of the originating study, new baseline assessments will be obtained. If during the period between Day 1 of this study and completion of the originating study no dose is received for greater than 3 consecutive days, an appropriate loading dose will be administered prior to continued maintenance dosing (see Section 11.3 for detail). Additional assessments that may not have been included in the prior EOT assessments are outlined in the Schedule of Assessments and will need to be completed prior to study drug administration.

Participants who participated in Part A of C5351004 or any other open label osivelotor study, will undergo safety and outcome assessments at Baseline (Day 1) and every 12 weeks thereafter (Table 2).

Participants from Part B of C5351004, or any other randomized, blinded, placebo controlled osivelotor study will undergo safety and outcome assessments at Baseline (Day 1), Week 8, Week 16, Week 24, and every 12 weeks thereafter (Table 3).

Pediatric participants from Part C of C5351004 will undergo safety and outcome assessments at Baseline (Day 1), Week 2, Week 4, Week 8, Week 12, Week 16, Week 20, Week 24, and every 12 weeks thereafter (Table 4).

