## 5.3. Justification for Dose

The daily maintenance dose for adults in the open label extension study will be 150 mg, which was the optimal efficacious dose determined from Part A of C5351004. The daily maintenance dose for all adult participants who have already enrolled in C5351005 prior to this amendment may be adjusted to 150 mg.

Adolescent and pediatric participants from C5351004 Parts B and C will be administered a dose that provides generally equivalent exposure to adult participants.

Further modifications to the loading doses may be made based on cumulative data from a population PK (PPK) model. Additionally, if there are safety/tolerability issues or lack of biomarker response at higher doses in the originating study, a drug dose reduction may be instituted as noted in Section 11.3.

The methodology for loading dose selection used in this open label study will differ for participants completing Parts A, B, and C of C5351004 and are shown in Section 11.3 and Table 6. For participants from the parent study who have been off study drug treatment greater than 3 consecutive days prior to enrolling into this study, a new loading dose regimen will be initiated as shown in Section 11.3.

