### 6.1. Inclusion Criteria

Participants must meet all inclusion criteria to be eligible for study participation.

1. Aged 6 months or older with SCD who participated and received study drug in an osivelotor clinical study and completed the EOT visit.

Note: Participants who discontinued study drug in the originating study due to an AE, but who remained on study, may be eligible for treatment in this study provided the AE does not pose a risk for treatment with osivelotor. Also, participants who completed treatment from the originating study but were not able to rollover into C5351005 due to delay in study site activation will be eligible provided other eligibility criteria are met.

2. Females of child-bearing potential are required to have a negative urine pregnancy test prior to dosing on Day 1.

Note: Females who become of child-bearing potential during the study must be willing to have a negative urine pregnancy test to remain in the study.

3. If sexually active, females of child-bearing potential must consistently use highly effective methods of contraception consistently throughout the study and for at least 84 days after the last dose of study drug. Male participants are eligible to participate if they agree to the following requirements during the study intervention period and for 84 days after the last dose of study intervention, which corresponds to the time needed to eliminate reproductive safety risk of the study intervention:

- Refrain from donating sperm

PLUS either:

- Be abstinent from heterosexual intercourse as their preferred and usual lifestyle (abstinent on a long-term and persistent basis) and agree to remain abstinent.

OR

- Must agree to use a male condom when engaging in any activity that allows for passage of ejaculate to another person.

A male participant should be advised of the benefit for a female of child-bearing potential partner using a highly effective method of contraception with a failure rate of <1% per year.

4. Has provided written informed consent/assent. For underage participants, both the consent of the participant's legal representative or legal guardian and the participant's assent (where applicable) must be obtained based on local requirements.

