**Table 14. Modified Loading Dose for Those with a Gap in Treatment from C5351004 Part A, Part B, and Part C**

Amount of Consecutive Days with Missed Doses	100 mg Maintenance Dose	150 mg Maintenance Dose	200 mg Maintenance Dose
>3 to <7 consecutive days of missed doses	200 mg QD x 3 days	300 mg QD x 3 days	300 mg QD x 4 days
7 to <14 consecutive days of missed doses	200 mg QD x 5 days	300 mg QD x 5 days	300 mg QD x 7 days
14 to <42 consecutive days of missed doses	200 mg QD x 7 days	300 mg QD x 7 days	300 mg QD x 10 days
42 consecutive days of missed doses or greater	200 mg QD x 7 days	300 mg QD x 7 days	300 mg QD x 14 days

Abbreviations: BID, twice daily; QD, once daily.

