## **Appendix 1.2. Baseline Derivations**

### **Baseline derivation for labs, EPO, pharmacodynamic endpoints, weight and vital signs**

1. If the gap between EOT visit (EOT CRF form) from parent study and study day 1 from OLE study is  $< 7$  days (date of first dose of study drug in OLE – EOT visit date from parent study + 1  $< 7$ ), use Week 12 analysis visit assessment from the parent study to serve as the baseline. If this assessment is not available, baseline is set to missing.
2. If the above defined gap in #1 is  $\geq 7$  days, use the latest pre-dose day 1 assessment from OLE study to serve as the baseline.

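### The parent EOT date behind the SAP's 42-day and 7-day gap rules is undefined, and the formula's added day puts both cut-offs out of step with the protocol

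*SAP*

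**What the plan says.** **SAP.** One formula serves two purposes. Section 5.3 (and 2.2.3 in substance) forms the delayed-start group from a "gap in dosing > 42 consecutive days from completing the originating study (Date of first dose in C5351005 – EOT date" of the parent study, plus 1); the condition in full is "Date of first dose in C5351005 – EOT date from parent study + 1 > 42". Appendix 1.2 computes "date of first dose of study drug in OLE – EOT visit date from parent study + 1" and compares it with 7. Below 7, the baseline is the parent Week 12 assessment, or missing if there is none. At 7 or more, it is the latest pre-dose Day 1 assessment in the extension.

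The date subtracted is called the EOT date in 2.2.3 and 5.3, and the EOT visit date in Appendix 1.2, which points to the EOT CRF form. The SAP does not say whether the parent form records a visit or the last dose. For the extension's own form, SAP 5.1 and 6.2.1 treat the EOT date as the last dose.

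**Protocol.** Table 1 is for starts delayed by more than 42 days. New baseline assessments are taken when Day 1 is more than 7 days after parent completion (5.1 and the note to Table 2; SAP 2.2.3 repeats this). Table 2 marks no hematology or chemistry at baseline. On eligibility, inclusion criterion 1 states: "Participants who discontinued study drug in the originating study due to an AE, but who remained on study, may be eligible for treatment".

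Time off drug is counted in two ways. The Synopsis and 5.1 ask whether "during the period between Day 1 of this study and completion of the originating study no dose is received" for more than 3 days, and 9.2 also counts from completion. Section 5.3 covers parent-study participants "who have been off study drug treatment greater than 3 consecutive days prior to enrolling into this study", 3.2.1 speaks of being off drug before enrolling, and Table 14 counts missed doses, its longest row being "42 consecutive days of missed doses or greater".

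**The concern.** A participant who stopped parent drug for an adverse event but stayed on study accumulates off-drug time before parent completion. A gap that starts at the parent EOT visit does not see that time. Such a participant could be tabulated without delayed start after a longer washout than others in the delayed-start columns. SAP 6.4 plans no subset analysis that would separate them.

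Independently, adding 1 to a date difference changes who falls on each side of 42 and 7 days. At the 7-day limit the SAP may look for a Day 1 laboratory value that the protocol did not ask the site to collect. The secondary endpoints on hemoglobin, reticulocytes, LDH and unconjugated bilirubin are changes from that baseline.

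**Working it through.** **1. The two cut-offs.** Let d = first extension dose date − parent EOT date. The SAP value is d + 1.

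| d | SAP value | SAP result | Protocol, on date difference |
|---|---|---|---|
| 41 | 42 | not delayed | not above 42 |
| 42 | 43 | delayed | not above 42: **conflict** |
| 43 | 44 | delayed | above 42 |
| 5 | 6 | parent Week 12 baseline | no new baseline |
| 6 | 7 | extension baseline | no new baseline: **conflict** |
| 7 | 8 | extension baseline | no new baseline: **conflict** |
| 8 | 9 | extension baseline | new baseline |

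Dropping the 1 cures d = 42 and d = 6. It does not cure d = 7, because Appendix 1.2 sends a value of exactly 7 to the extension baseline while the protocol requires more than 7. The inequality has to change as well.

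If the EOT date was itself a dosing day, full days without a dose number d − 1. Then d = 42 is 41 dose-free days and d = 43 is 42. The first meets neither the more-than-42 gap of Protocol 9.2 nor the 42-or-more row of Table 14. The second meets Table 14 only.

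**2. The early stopper.** Assumptions: EOT visit on parent Day 84 (Part A lasts 12 weeks, Protocol 3.1), extension Day 1 on the same day, half-life 10 days (Protocol 3.1, SCD patients). The fraction of drug remaining is 2^(−t/10), where t is days since the last dose.

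| Last parent dose | SAP value, EOT = visit | Same formula from last dose | Dose-free days | Drug remaining |
|---|---|---|---|---|
| Day 84 | 1 | 1 | 0 | 100% |
| Day 70 | 1 | 15 | 13 | 37.9% |
| Day 56 | 1 | 29 | 27 | 14.4% |
| Day 42 | 1 | 43 | 41 | 5.4% |
| Day 28 | 1 | 57 | 55 | 2.1% |
| Day 14 | 1 | 71 | 69 | 0.8% |

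The class changes only for a last dose by about Day 42. It is Day 42 with the added day (42 + 1 = 43), Day 41 on a plain difference (84 − 41 = 43), and Day 40 on dose-free days (84 − 40 − 1 = 43). If Day 1 falls 14 days after the EOT visit, the SAP formula crosses at Day 56 (98 − 56 + 1 = 43).

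**3. One date cannot serve both rules.** Take the Day 28 stopper. If EOT means the visit, the baseline is the same-day parent value, which is sensible, but the group hides 55 dose-free days. If EOT means the last dose, the value is 57 and the group is right. Appendix 1.2 then wants an extension pre-dose value, although Day 1 coincides with parent completion, no new baseline is triggered, and Table 2 schedules no baseline hematology or chemistry.

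**4. The protocol passages.** For the same stopper with same-day roll-over, no days lie between completion and Day 1, so the loading-dose condition in the Synopsis and 5.1 is not met, while that in 5.3 is. Under 9.2 with Table 2 the first visit after baseline is Week 12. Under 3.2.1, participants who were off drug are seen every 2 weeks up to Week 8.

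**The case against.** The best defense is that the SAP's own usage makes the EOT date the last dose. If the parent form works that way, or if someone stopping for an adverse event has the EOT visit when drug stops, the Day 28 example is classed as delayed and the grouping problem disappears. That stands as a possibility. The visit reading is better supported: SAP 5.3 says from completing the originating study, Appendix 1.2 names a visit, SAP Table 5 ties EOT to Week 12, and the 5.1 and 6.2.1 definitions concern the extension. The documents do not settle it.

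It is also fair that the groups follow the two visit schedules, which Protocol 9.2 triggers from completion. Regrouping by last dose could put participants seen every 12 weeks under windows for early visits they never had. Moving the baseline rule to last dose could discard the same-day parent value for the very participants at issue. Both objections stand and shape the fix.

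A reader might infer that re-challenged participants are presented as continuously treated. The documents do not support that: the label is without delayed start, and the group openly includes gaps up to 42 days. Nor are early adverse events hidden. TEAEs are not assigned to visit windows, they are also tabulated for all participants, and every AE is listed.

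An inclusive day count is a legitimate convention, but it does not match the protocol limits it is meant to apply.

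**Conclusion.** The point holds in two parts. First, the added day, together with the strict 7-day inequality, is inconsistent with the protocol on a plain reading of dates. One date difference (42) is misplaced at the group cut-off and two (6 and 7) at the baseline cut-off; the latter can leave hemoglobin, reticulocyte, LDH and bilirubin baselines missing. Whether any participant has those differences is not stated.

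Second, the undefined parent EOT date allows a participant with more than 42 days off drug to be summarized without delayed start. This is conditional on the visit reading, on stopping by about Day 42 under same-day roll-over, and on such participants existing. Their number is not given and may be zero.

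A reader might go further and infer a known bias in mean hemoglobin change. That would need an assumed stopping week, arm size and hemoglobin recovery that the documents do not supply for this study. SAP 5.2 plans no hypothesis test, so the effect is confined to descriptive grouping and change from baseline. The protocol contradiction over time off drug stands whichever EOT reading applies.

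**What to change.** 1. In SAP 2.2.3, 5.3 and Appendix 1.2, define the parent EOT date and drop the added day. In Appendix 1.2, also use the parent value up to and including 7 days and the extension value above 7, so that both limits match the protocol.
2. Keep the baseline branch and visit windows tied to parent completion and the schedule actually followed. The same-day parent value then stays the baseline for same-day roll-over.
3. Derive a separate dosing gap: first extension dose date − last parent-study dose date − 1, in full days without a dose. Use it to flag, list or separately summarize participants who stopped parent drug early, and report how many there are.
4. In the protocol, reconcile the Synopsis, 5.1 and 9.2, which count from parent completion, with 3.2.1, 5.3 and Table 14, which count time off drug or missed doses. No dose or visit rule is proposed here.

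The cost is SAP wording, a small change to the gap derivation, one derived date from the parent database (which SAP 3.4 already draws on), and a protocol clarification.
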